7.9.3.9 Battery longevity

The Percept PC system has the ability to estimate the battery longevity based on programmed stimulation settings. This projected battery longevity will be determined from the JSON session data at each respective evaluation phase, and a subject will be considered a success if they have a projected battery longevity that is at least 25% greater within the respective aDBS visit as compared with the cDBS visit.

Missing values

Missing data imputation will not be performed for the battery longevity objective.

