Evidence from single center feasibility studies has demonstrated that aDBS is at least as efficacious as cDBS based on UPDRS III motor scores and could potentially be up to 27% more effective.^{47,48,49} aDBS may also reduce stimulation-induced adverse effects such as dyskinesia and speech impairment. In multiple studies, PD patients receiving aDBS showed less dyskinetic effects compared to cDBS, potentially by reducing the sum effect of stimulation and medication.^{25,52,54} Regarding speech, one study of 10 subjects showed a clinically meaningful improvement in speech intelligibility with aDBS over cDBS.⁵⁰ Overall aDBS was well tolerated in freely moving PD subjects both On and Off medications for up to 8 hours.^{47,49,52,53,55} In addition, multiple studies showed a significant reduction in the power usage with aDBS compared to cDBS, averaging about 50% of the power demand of standard cDBS Therapy.^{45-49,52,54}

Medtronic Business Restricted

Although the subjects and conditions of the individual studies assessing aDBS vary, these studies have consistently shown the feasibility of using aDBS controlled by STN beta LFP feedback and its potential to effectively reduce PD symptoms while reducing side effects and increasing battery longevity.

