4.1.4. Additional Objectives

To characterize aDBS as compared to cDBS (Primary Cohort):

- Voice Handicap Index (VHI): “best” and “worst” conditions
- MDS-UPDRS III subscore (On stim/On med) of tremor, rigidity, and bradykinesia questions where a side can be determined: 3.3 b, c, d, e (rigidity), 3.4 a, b (finger taps/bradykinesia), 3.15 a, b (postural tremor of hands), 3.16 a, b (kinetic tremor of hands), and 3.17 a, b, c, d (rest tremor amplitude)

Medtronic Business Restricted

- MDS-UPDRS III (On stim/On med)
- MDS-UPDRS II: “best” and “worst” conditions
- MDS-UPDRS III speech question (On stim/On med) q 3.1
- MDS-UPDRS IV
- EQ-5D-5L
- PDSS-2
- Data collected from wearable (for example: % of wear time tremor was detected, Dyskinesia Score [DKS], Bradykinesia Score [BKS], Fluctuation and Dyskinesia Score [FDS])
- PDQ-39 Summary Index (SI) and subscores: mobility, activities of daily living, emotional well-being, stigma, social support, cognition, communication, bodily discomfort
- PDQ-39 speech questions 34 and 35
- % of subjects with at least 25% increase in projected battery longevity as compared with cDBS
- Parkinson’s Disease Home Diary: “On” time without troublesome dyskinesia, “On” time without dyskinesia, “On” time with non-troublesome dyskinesia, “On” time with troublesome dyskinesia, “Off” time, and Asleep time.
- Patient preference of aDBS vs cDBS (as assessed by a Medtronic-developed patient preference questionnaire)
- Patient satisfaction with aDBS (as assessed by a Medtronic-developed patient satisfaction questionnaire)
- Device data from JSON file including BrainSense data

Subgroup analyses (from the entire study population):

- For those with dyskinesias: at least 25% of time: Wearable data
- For those with speech side effects: VHI
- For those with mixed programming (one hemisphere with aDBS and one with cDBS): MDS-UPDRS III by side
- For those who use event markers in long-term follow-up: characterize subject population and satisfaction with use of event markers
- For those who finished the aDBS Evaluation Phase: one aDBS mode will be selected per subject based on subject preference or programming availability at the end of the aDBS Evaluation Phase. The aDBS Evaluation Phase results may be characterized based on the selected mode.

Medtronic Business Restricted

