8.4. Exclusion Criteria

A potential subject who meets any of the following criteria will be excluded from participating in the study:

General (Primary Cohort):

1. Subject and/or caregiver is unable to utilize the patient programmer
2. Subject has more than one lead in each hemisphere of the brain
3. Subject has cortical leads or additional unapproved hardware implanted in the brain
4. Subject has more than one INS
5. At enrollment, the subject's INS has a predicted battery life of <1 year
6. Subject has Beck Depression Inventory II (BDI-II) > 25
7. Subject requires diathermy, transcranial magnetic stimulation (TMS), or electroconvulsive therapy (ECT)
8. Subject has a metallic implant in the head, (eg, aneurysm clip, cochlear implant)
9. Subject has, or plans to obtain, an implanted electrical stimulation medical device anywhere in the body (eg, cardiac pacemaker, defibrillator, spinal cord stimulator)
10. Subject has, or plans to obtain, an implanted medication pump for the treatment of Parkinson's disease (eg, DUOPA™ infusion pump) and/or portable infusion pump
11. Based on the opinion of the investigator, the subject has an abnormal neurological examination that would preclude them from study participation
12. Subject is breast feeding
13. Subject is under the age of 18 years
14. Subject is currently enrolled in or plans to enroll in any concurrent drug and/or device study that may confound the results of this study as determined by the Medtronic study team
15. Subject is unable to use or tolerate wearable
16. Subjects with signal artifact on all 6 aDBS sense pathways (3 each on both DBS leads) which preclude the clinician from setting thresholds

General (Directional Stimulation Cohort):

General exclusion criteria for the Directional Stimulation Cohort are the same as for the Primary Cohort.

9. Study Procedures

The study schedule, procedures, and methods of assessment are defined in detail to enable compliance with the required activities, and to ensure that the resulting data meet the criteria for evaluability [Figure 4](#). Case report forms (CRFs) will be provided for use in collecting data for all subjects; the pertinent CRFs along with the applicable source documentation will be completed for each subject at the time of each

Medtronic Business Restricted

[figure not shown]
study visit. Subjects enrolled in the Directional Stimulation Cohort will follow the same study schedule, procedures and methods of assessment.

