9.3. Scheduled Follow-up Visit Windows

Data analyses include follow-up visits, regardless of whether the visit occurs within the window. Therefore, a late visit is preferred over a missed visit but must be accompanied by a deviation report. Follow-up visit windows are listed in [Table 4](#). Should a subject miss a visit or the visit falls outside the pre-specified window, a study deviation must be reported and the original follow-up schedule maintained for subsequent visits.

Table 4: Visit Windows

Visit	Visit ranges
LFP Screening	1-45 days after enrollment
cDBS Baseline	30-45 days after LFP Screening
aDBS Setup	1-45 days after Baseline
aDBS Adjustment	0-60 days after aDBS setup complete
Randomization / Day 0	No greater than 60 days after aDBS setup complete
aDBS Evaluation Visit 1	30-45 days after Day 0
aDBS Evaluation Visit 2*	30-45 days after Evaluation visit 1
Visit 3	45-60 days after Evaluation Visit 2 (or Evaluation Visit 1 if the subject is only configured to one aDBS mode)
Visit 4	45-60 days after Visit 3
Visit 5	90 +/- 14 days after Visit 4
Visit 6	90 +/- 14 days after Visit 5
Extended Access Visits	Every 180 +/- 60 days beginning after Visit 6 and every 6 months thereafter following the previous extended access visit

* If two aDBS modes are set up

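### The battery objective compares longevity projections taken 31 to 195 days apart; if the projection is remaining life, a true 25% gain is always scored a failure

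*SAP*

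**What the plan says.** Protocol 4.1.4 lists among the additional objectives the percentage "of subjects with at least 25% increase in projected battery longevity as compared with cDBS". SAP 7.9.3.9 turns this into a rule for each subject: success is a "projected battery longevity that is at least 25% greater within the respective aDBS visit as compared with the cDBS visit".

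On the measurement itself the SAP says: "The Percept PC system has the ability to estimate the battery longevity based on programmed stimulation settings". On its source: "This projected battery longevity will be determined from the JSON session data at each respective evaluation phase". It does not say whether the figure is life remaining on that date, and it makes no allowance for time passing between the two readings. I take the cDBS visit to be the cDBS Baseline visit, which SAP 7.9.2.3.2 names for the energy (TEED) calculation.

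The closest the documents come to defining such a projection is exclusion criterion 5 in Protocol 8.4: "At enrollment, the subject's INS has a predicted battery life of <1 year".

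**The concern.** The neurostimulator is already implanted and running on its battery when the subject enrols. If the projection is remaining life, it falls with the calendar even when drain does not change. A later aDBS reading is then set against an earlier cDBS reading, and the depletion in between counts against aDBS.

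The effective bar would sit above 25%. It would vary with the age of the battery and with how long setup and adjustment took, and neither is an effect of aDBS. Within a crossover subject, the mode given second would face the higher bar. Energy savings are a stated potential benefit (Protocol 10.3), and data through the Evaluation Phase go into the approval submissions (Protocol 13.2.7), so the reported percentage will be read.

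**Working it through.** The plan gives no expected rate or power for this objective, so there is no stated figure to reproduce.

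**Interval between readings (Protocol Table 4).**
- Baseline to aDBS Setup: "1-45 days after Baseline".
- Setup to Day 0: "No greater than 60 days after aDBS setup complete", so 0 to 60 days.
- Day 0 to Evaluation Visit 1: 30 to 45 days.
- Evaluation Visit 1 to Visit 2: 30 to 45 days.

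Visit 1 is therefore 1 + 0 + 30 = 31 to 45 + 60 + 45 = 150 days after Baseline. Visit 2 is 31 + 30 = 61 to 150 + 45 = 195 days after Baseline. Protocol 9.3 keeps out-of-window visits in the analysis, so some gaps may be longer.

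**Model if the projection is remaining life.** Let L be the life left at Baseline at cDBS drain, tc the days from Baseline to Setup on cDBS, ta the days on aDBS from Setup to the visit, and g the true proportional gain in longevity. At Setup, L − tc remains at cDBS drain, which is (1 + g)(L − tc) at aDBS drain. At the visit, (1 + g)(L − tc) − ta is left. So:

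- observed ratio = [(1 + g)(L − tc) − ta] / L
- at g = 0.25, this is 1.25 − (1.25 tc + ta) / L, which is below 1.25 for any positive interval
- gain needed to pass = (1.25 L + ta) / (L − tc) − 1

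Example with L = 1 year (365.25 days), tc = 45, ta = 150: ratio = (1.25 × 320.25 − 150) / 365.25 = 250.3 / 365.25 = 0.69. Gain needed = (456.6 + 150) / 320.25 − 1 = 89%.

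The documents give no distribution for L, so it is an assumption shown over a range. The intervals are 31 days (tc 1, ta 30), 150 days (tc 45, ta 105) and 195 days (tc 45, ta 150).

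| L (years) | Ratio for a true 25% gain: 31 / 150 / 195 days | True gain needed to pass: 31 / 150 / 195 days |
|---|---|---|
| 1 | 1.16 / 0.81 / 0.69 | 34% / 75% / 89% |
| 3 | 1.22 / 1.10 / 1.06 | 28% / 40% / 45% |
| 5 | 1.23 / 1.16 / 1.14 | 27% / 34% / 37% |
| 8 | 1.24 / 1.19 / 1.18 | 26% / 31% / 32% |

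**If the projection depends on settings alone,** the ratio is 1 + g whatever the interval. A true 25% gain reads as 1.25 and passes.

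**The case against.** The main objection is that the documents never define the field as remaining life. A figure based on programmed settings could be a projection from a standard battery state, in which case dates do not matter. Exclusion criterion 5 uses a different term, for eligibility, and does not define the analysis variable. This stands, so the point has to be conditional. Even so, remaining life is the likelier meaning: a threshold of one year applied at enrollment to a device already in use screens out little unless it means life left, and a remaining-life estimate also needs the settings.

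The second objection is low consequence. SAP 7.9.3 plans no hypothesis test for the additional objectives. The secondary TEED endpoint has no battery-age term. Any bias works against the sponsor's device, so it cannot create a false claim of benefit. With several years of battery left and a short interval, only gains just above 25% are misclassified. All of this stands.

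Two stronger inferences are tempting, and the documents do not support them:

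- A reader might infer that even a large saving would be scored a failure. Protocol 3.1 cites aDBS as "averaging about 50% of the power demand of standard cDBS Therapy". If the whole interval is charged at cDBS drain, halved drain with 12 months left reads as +18% at 150 days and −7% at 195 days. But the Evaluation Phase is spent on aDBS, and subjects needing adjustment go home in an aDBS mode (Protocol 9.9.1). With aDBS drain from Setup, the readings are (2 × 320.25 − 105) / 365.25 = 1.47 and (2 × 320.25 − 150) / 365.25 = 1.34. Both pass.
- A reader might infer that one mode is systematically penalised. The second-period penalty is real within a subject, but sequence is randomised for two-mode subjects, which largely balances it between modes.

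**Conclusion.** The point holds conditionally. It is certain that the SAP compares two unadjusted projections that Table 4 places 31 to 195 days apart, and that it does not say what the projection measures. If it measures remaining life, which is likelier than not but unproven, every true gain of exactly 25% is scored a failure. The real bar is then 26% to 32% with 8 years left, rising to 34% to 89% with 1 year left. These figures assume in-window visits, cDBS drain up to Setup, a single aDBS drain afterwards, and the stated starting lives.

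The documents do not support saying as fact that depletion is charged to aDBS. The effect is confined to one descriptive percentage; the primary and TEED analyses are untouched.

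**What to change.** State in SAP 7.9.3.9 whether the projected-longevity field is remaining life at interrogation.

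- **If it is,** score success when (aDBS-visit projection + days on aDBS since Setup) is at least 1.25 × (cDBS Baseline projection − days from Baseline to aDBS start), all in the same time unit. Alternatively, compare both settings' projections at the same battery state. In the model above the left side equals (1 + g)(L − tc), so the rule passes exactly when g is at least 25%. For L = 1 year at 195 days with a true 25% gain: 250.3 + 150 = 400.3 against 1.25 × 320.25 = 400.3.
- **If it is settings-only,** keep the current ratio. An elapsed-time adjustment would then introduce a bias.

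Subtracting the whole interval from the Baseline projection is simpler but overcorrects. Its effective bar is 1.25 − 0.25 ta / (L − tc), so at 195 days it would pass a true gain of about 13% with 12 months left and about 20% with 24 months left.

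The cost is a sentence or two in the SAP; the dates and projections are already collected. The downside is small: for the second-period mode, days on aDBS include time on the other mode, so the correction is approximate there.

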7.9.3.10 Patient Satisfaction

Patient satisfaction with aDBS during the long-term follow-up phase will be assessed by a Medtronic-developed questionnaire. Part I of the questionnaire is displayed in Figure 7-4, and Part II is displayed in Figure 7-5.

Figure 7-4. Patient Satisfaction Questionnaire, Part I

Instructions: We are interested in your satisfaction with the adaptive deep brain stimulation (DBS) therapy you received during the long term follow up phase of this study (approximately the past 9-10 months). Think about how effective the therapy was on your disease-related symptoms (examples: shaking, slowness, stiffness) and any side effects (examples: trouble swallowing, change in mood, tingling) caused by the DBS therapy you received. For each question, please place a single check mark next to the response you feel best represents how you would answer the question.

Would you recommend adaptive DBS to other DBS patients with Parkinson's Disease

- Definitely yes.
- Probably yes.
- Neutral.
- Probably not.
- Definitely not.

Overall how satisfied or unsatisfied are you with the adaptive DBS you received during the long term follow up phase of this study

- Very satisfied.
- Somewhat satisfied.
- Neutral
- Somewhat unsatisfied.
- Very unsatisfied.

What specific movement symptom was the most improved by adaptive DBS therapy

- None
- Speech
- Chewing and swallowing
- Handwriting
- Tremor.
- Walking and balance
- Freezing
- Stiffness / Rigidity
- Slowness & hesitancy during movement / bradykinesia
- Involuntary, random movements / dyskinesia
- Posture
- Cramps or spasms / dystonia
- Other

If Other, Specify _____

Figure 7-5. Patient Satisfaction Questionnaire, Part IISection II: Satisfaction with Event Markers

Instructions: During the study, you may have used your patient programmer to capture your experience outside the clinic, such as recording dyskinesia, tremor, rigidity, freezing, sleep disturbance or taking PD medications. This feature is called "Event Markers" and we are interested in your experience with it.

NA, Subject is on CIP v2.0

1. Overall, how satisfied are you with Event Markers?

- Very satisfied
- Somewhat satisfied
- Neutral
- Somewhat unsatisfied
- Very unsatisfied
- Did not use

2. How easy did you find the Event Markers to use?

- Very easy to use
- Somewhat easy to use
- Neutral on ease of use
- Somewhat difficult to use
- Very difficult to use
- Did not use

3. How do you think use of Event Markers impacted how you communicated your experience between clinic visits with your study doctor?

- Event Markers significantly improved communication with my physician
- Event Markers somewhat improved communication with my physician
- Event Markers did not impact communication with my physician
- Event Markers did not improve communication with my physician
- Did not use

Missing values

Missing data imputation will not be performed with the patient satisfaction objective.

7.9.3.11 Device data

The parameters summarized with the device data from the JSON file may include, but are not limited to:

- Active contacts
- Minimum and maximum voltage or current, per subject, for each aDBS Evaluation Phase
- Distribution of stimulation parameters
- Subjects tolerating aDBS for each aDBS mode
- Use of event markers in long-term follow-up
- aDBS on time
- aDBS Method parameters by visit
 - Decreasing ramp rate
 - Increasing ramp rate

- Lower stimulation limit
- Upper stimulation limit
- BrainSense data
 - LFP streaming data by therapy mode (cDBS, aDBS Single Threshold Mode, and aDBS Dual Threshold Mode)
 - LFP peak tracker
 - Peak Categories
 - Beta
 - Tremor
 - Gamma
 - Other
 - Peak amplitude
 - Peak frequency
 - Time spent below, between, and above thresholds for every group
 - Top LFP bipolar pair for each patient
- Circadian Rhythm tracker
 - Identify patients with circadian rhythms
 - Track the number of hours spent below daytime mean (7am-10pm) during nighttime (10pm-7am)

BrainSense data will be analyzed by the Medtronic Research and Technology group, or designee. Key BrainSense analyses will be presented in the final clinical study report.

A subgroup analysis will be performed to characterize the subject population and satisfaction with the use of event markers among subjects who use event markers during long-term follow-up.

Missing values

Missing data imputation will not be performed for the device data objective.

7.10 Safety Evaluation

The safety assessment is to characterize:

- Stimulation-related adverse events during the aDBS evaluation and the cDBS baseline phases.
- Serious adverse events, adverse events, and device deficiencies throughout the study.

Stimulation-related adverse events will be summarized during the cDBS Baseline and aDBS Evaluation Phases for all subjects, with tabulations individualized by aDBS mode in the Primary Cohort, by target site in the Primary Cohort, by lead type in the Primary Cohort, and the Directional Stimulation Cohort (DSAT analysis set). Summarized results from the Directional Stimulation Cohort will be provided as supporting analyses to the Primary Cohort results. In the Primary Cohort, if statistical comparisons of poolability across mode, lead type, and target site are accepted, overall tabulations will be provided as appropriate. To test for a difference in safety by target site (STN/GPi) and lead type, Fisher's exact test will be computed testing for differences between target sites and between lead type in the proportion

of subjects with a stimulation-related adverse event during the aDBS Evaluation Phase using data from both periods. [REDACTED]

[REDACTED]

[REDACTED]

[REDACTED]

A repeated measures logistic regression will be used to test for a difference between aDBS modes in the proportion of subjects with stimulation-related adverse events in the randomized subjects who enter the aDBS evaluation phase in the Primary Cohort. [REDACTED]

[REDACTED]

[REDACTED]

[REDACTED]

[REDACTED]

[REDACTED]

P-values >0.1 will be deemed as supporting the assumption of no target site, lead type, or mode effect, respectively, and the data will be considered poolable across the respective variable. If the p-value approaches statistical significance (defined as ≤ 0.1),¹ safety summaries will not be provided as a combined summary for that variable.

Serious adverse events, adverse events, and device deficiencies that occur from the time of enrollment through study exit/discontinuation will be summarized for all enrolled subjects. Analyses will be conducted on the AT analysis set for subjects in the Primary Cohort and on the DSAT for subjects in the Directional Stimulation Cohort. The denominator will include the appropriate number of subjects for each respective phase, period, and cohort. Events will be summarized by number of events, number of subjects who experienced the event, and percentage of subjects who experienced the event.

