	
 • Long-Term Follow Up Phase: Four visits in preferred aDBS mode for approximately 10 months • Extended Access Phase: Additional visits in the preferred aDBS mode every 6 months through commercial approval of aDBS
Randomization	Randomization to a crossover sequence of aDBS single threshold and aDBS dual threshold modes
Sample Size	
Primary Cohort
 
It is estimated that approximately 70-100 subjects implanted with a commercially available Medtronic DBS system with Percept PC INS will be enrolled in the study to obtain 40 subjects for whom at least 1 aDBS mode is acceptable and who enter the aDBS evaluation phase. It is expected that approximately 50% of enrolled subjects will be exited from the study at LFP Screening due to insufficient Alpha - Beta band amplitude and/or artifact. Accounting for a 10% dropout during the aDBS Evaluation Phase, a minimum of 36 subjects (at least 8 per brain target) are expected to complete the aDBS Evaluation phase.
 
Because the device implant will occur outside of the study and the study requires participants to be stable on cDBS, the standard deviation of the change from cDBS to aDBS in "On" time without troublesome dyskinesia will be used to establish a threshold for assessing the performance goal. The threshold will be set as 1 standard deviation. If the difference between aDBS and cDBS (aDBS-cDBS) for a subject is at least -1 standard deviation, the threshold will be met for the subject. Using this threshold, the proportion of subjects who exceed the threshold will be computed.
 
The sample size was estimated using a binomial distribution for a one-sided test for a proportion to compare to a performance goal of 50%. Assuming the alternative hypothesis of 85% of subjects exceeding the threshold described above, a minimum of 36 subjects achieves at least 90% power to reject a performance goal of 50%. Sample size was computed in PASS 11.
 
For the safety analysis, a minimum of 30 subjects followed for approximately 30 days with aDBS out-of-clinic in the subjects' real-world environments provides greater than 95% probability that all stimulation-related adverse events with a true adverse event rate of at least 10% would be reported at least once.
 
Directional Stimulation Cohort
 
In addition, approximately 15 subjects implanted with a commercially available Medtronic DBS system with Percept PC INS and SenSight

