9.7. Enrollment and Screening Phase

This phase begins at consent and includes an Enrollment visit and an LFP Screening visit.

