- Beck Depression Inventory II (BDI-II)
- Pregnancy test (for female subjects of child-bearing potential)
- Device identification information, including historical DBS implant information
- Programming session upload to Medtronic via CDU, with BrainSense data included in the JSON session data report
- AE and device deficiency assessment

The clinician will ensure the INS device time matches that of the clinician programmer tablet (network enabled). If the INS time does not match the network time, the INS time will be updated.

The subject will be instructed on the use of the PD Home Diary. For at least 3 consecutive days in the 14 days prior to the cDBS Baseline and aDBS Evaluation visits, the subject will record, in 30-minute intervals, whether they were Asleep, “Off,” “On” without dyskinesia, “On” with non-troublesome dyskinesia, or “On” with troublesome dyskinesia. The subject will also be instructed on the use of the PKG Watch.

The subject will leave the visit on their current cDBS settings (including BrainSense settings).

9.8. cDBS Baseline Phase

This phase begins when the enrollment visit is complete and includes an LFP screening visit, cDBS Baseline period and cDBS Baseline visit.

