Appendix A - aDBS Global Impression of Change Score (GIC)

This scale is used to help assess for acceptability of an aDBS mode vs. cDBS for an individual subject. A lower number is better in terms of acceptability (ie, greater efficacy with minimal side effects).

- “Acceptable”: A selection appearing in the white (unshaded) boxes means the mode has been deemed “acceptable” and is available for selection for that subject in the aDBS Evaluation Phase. The subject may be programmed with this mode.
- “Unacceptable”: A selection appearing in the grey shading means the mode has been deemed “unacceptable” and is eliminated for selection in the aDBS Evaluation Phase. The subject will not be programmed with that mode.

To decide if a mode is acceptable to a subject, the following table will be used:

		Side effects		
Efficacy	None	Does not significantly interfere with patient's functioning	Significantly interferes with patient's functioning	Side effects experienced outweigh efficacy
Vast improvement	01	02	Fail:10	Fail:11
Decided improvement	03	04	Fail:12	Fail:13
Slight improvement	05	06	Fail:14	Fail:15
Unchanged	07	08	Fail:16	Fail:17
Worse	Fail:18	Fail:19	Fail:20	Fail:21

Medtronic Business Restricted

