7.1.3 Analysis Sets

All-Consented (AC): includes all subjects who properly signed the study-specific informed consent (IC). This patient set will be used to summarize patient disposition.

Full Analysis Set (FAS): includes all Primary Cohort subjects, using the intention-to-treat (ITT) principle, who initiate the aDBS Evaluation Phase using the randomized treatment assignment for each subject that was randomized and the programmable treatment assignment for those subjects that may only be configured to one aDBS mode (dual or single threshold).

As-Treated (AT): includes all Primary Cohort subjects who are treated with cDBS and/or aDBS during the cDBS Baseline Evaluation Phase and/or the aDBS Evaluation Phase, and Long-term Follow-up Phase and uses the observed treatment used for each subject in each phase.

All-Randomized (AR): includes all Primary Cohort subjects who were randomized in the aDBS Evaluation Phase, excludes those that were not configured to both modes.

Complete-Case (CC): FAS without imputation that includes all Primary Cohort subjects who have available measures for the respective analysis and are analyzed in their randomization group for those randomized or the programmable treatment for those configured to one aDBS mode.

Directional Stimulation As-Treated (DSAT): includes all Directional Stimulation Cohort subjects who have SenSight leads in a directional stimulation configuration who are treated with continuous Deep Brain Stimulation (cDBS) and/or adaptive Deep Brain Stimulation (aDBS) during the cDBS Baseline Evaluation Phase and/or the aDBS Evaluation Phase, and Long-term Follow-up Phase and uses the observed treatment used for each subject in each phase.

Directional Stimulation Complete-Case (DSCC): includes all Directional Stimulation Cohort subjects who completed the aDBS Evaluation Phase.

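### The cDBS and aDBS percentages for stimulation-related adverse events are not comparable: the aDBS group is a selected subset of the cDBS group, with different follow-up

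*SAP*

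**What the plan says.** SAP 7.10, like Protocol 13.6, says: "Stimulation-related adverse events will be summarized during the cDBS Baseline and aDBS Evaluation Phases for all subjects". The Protocol Synopsis assigns safety analyses to the As-Treated set. SAP 7.10 repeats this for the overall AE summary ("Analyses will be conducted on the AT analysis set for subjects in the Primary Cohort") and adds: "The denominator will include the appropriate number of subjects for each respective phase, period, and cohort". Under SAP 7.1.3 the As-Treated set "includes all Primary Cohort subjects who are treated with cDBS and/or aDBS during the cDBS Baseline Evaluation Phase and/or the aDBS Evaluation Phase", so a subject who never received aDBS still belongs to it.

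Two filters stand between the phases.

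- **LFP Screening.** The Synopsis expects that "approximately 50% of enrolled subjects will be exited from the study at LFP Screening".
- **The GIC.** Under Protocol 9.9.3 and Appendix A, a mode rated unacceptable "is eliminated for selection in the aDBS Evaluation Phase". Side effects that significantly interfere with functioning fail the mode at every level of efficacy. A subject with no acceptable mode is exited.

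The Protocol places LFP Screening in two phases. Section 9.8 says of the cDBS Baseline Phase: "This phase begins when the enrollment visit is complete and includes an LFP screening visit". Section 9.7 says of the Enrollment and Screening Phase: "This phase begins at consent and includes an Enrollment visit and an LFP Screening visit".

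**The concern.** The stimulation-related AE objective names the aDBS Evaluation and cDBS Baseline Phases together. Protocol 13.4.2 describes the aim of the study as benefit and safety similar to cDBS. Readers of the regulatory submission will therefore set the two percentages side by side.

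Those percentages would differ even if aDBS and cDBS carried the same risk. The cDBS figure includes people who never reached aDBS Evaluation. The aDBS figure has already lost the people who tolerated aDBS badly. Time at risk differs as well. No visible text plans a cDBS summary limited to the subjects who went on to aDBS. SAP 7.10 does use a common set once, for the mode-versus-mode test in randomized subjects, but not for cDBS against aDBS.

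**Working it through.** **Inputs.** Synopsis and Protocol 13.2.4: 70–100 enrolled, 40 entering aDBS Evaluation, 10% dropout, 36 completing. Synopsis: about 50% exit at LFP Screening. Protocol Table 4: LFP Screening 1–45 days after enrollment, Baseline visit 30–45 days after that, each aDBS evaluation period 30–45 days. Protocol 6.1.2: 70 patients entering aDBS Setup.

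**1. The plan's own funnel.** 36/(1 − 0.10) = 40, as stated. 40/(1 − 0.50) = 80, inside 70–100. At the lower end, 70 × 0.50 = 35, which is below 40, so a 50% exit fits only about 80–100 enrolled.

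**2. Overlap if LFP exits count in the cDBS phase (Protocol 9.8).**
- 80 enrolled: 40/80 = 50% of the cDBS group is also in the aDBS group.
- 100 enrolled: 50 pass LFP Screening, 10 more are lost at Setup or GIC, and 40/100 = 40%.

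**3. Overlap if they do not count (Protocol 9.7).** The cDBS group is the 40–50 who pass, so the overlap is 40/40 = 100% to 40/50 = 80%. At 80 enrolled, the choice of section moves the cDBS denominator between 80 and 40.

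**4. The Setup figure.** Assume the 70 covers both cohorts, with 85–115 enrolled (70 + 15 to 100 + 15). Exit before Setup is then 1 − 70/85 = 18% to 1 − 70/115 = 39%. Loss at Setup or GIC is 1 − (40 + 9)/70 = 30%. If 9 to 15 of the 70 are directional-cohort subjects, 55–61 are Primary Cohort, and the narrow-reading overlap falls to 40/61 = 66% to 40/55 = 73%. This picture has fewer LFP exits and more selection at Setup or GIC.

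**5. Composition alone (assumed risks).** Take 80 enrolled, equal follow-up, and a 10% risk for the 40 evaluated subjects under both therapies. The cDBS percentage is (40 × 10% + 40 × r)/80, where r is the risk in the other 40:

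| r | cDBS summary | aDBS summary |
|---|---|---|
| 5% | 7.5% | 10% |
| 20% | 15% | 10% |
| 30% | 20% | 10% |

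**6. Follow-up alone (assumed constant hazard, 10% per 30 days, the same for everyone).** Counted from enrollment, continuers have 1 + 30 = 31 to 45 + 45 = 90 days on cDBS. Use rounded mid-window values: 23 days for LFP exits, 60 for continuers, 38 for one aDBS mode. Risk at d days is 1 − 0.9^(d/30).
- LFP exits: 7.8%. Continuers: 19.0%. One aDBS mode: 12.5%.
- cDBS over all 80: (7.8% + 19.0%)/2 = 13.4%.
- Matched on subjects only: 19.0% on cDBS against 12.5% on aDBS, with no true difference.

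The last line shows that matching subjects without reporting exposure would not be enough.

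**The case against.** The best case for the plan is that it promises no comparison. The safety objective is to characterise events in each phase. The additional objectives refer to a comparison with cDBS; the safety objective does not. No test, ratio or side-by-side layout is specified, and the phase-specific denominators are disclosed. This stands, and it limits the point to interpretation. It does not make the two percentages comparable, and the stated aim of similar safety invites that use.

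Three stronger readings are tempting, and the documents do not support them.

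- **The two summaries describe different people.** They are nested: every subject in aDBS Evaluation has passed through the cDBS Baseline Phase.
- **Half the cDBS group will be LFP exits.** That is a planning expectation for enrolled subjects. It does not fit 70 enrolled, and the Setup figure in Protocol 6.1.2 points to fewer LFP exits.
- **The bias runs one way.** GIC selection favours aDBS. Short follow-up of LFP exits lowers the cDBS percentage, longer follow-up of continuers raises it, and the underlying risk of the exits is unknown.

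On the phase boundary, Protocol 9.7 stands against the Synopsis, Section 5, Section 5.1, Table 3 and Section 9.8, all of which place LFP Screening or the LFP exits in the cDBS Baseline Phase. The wider reading is therefore the likelier one. On the narrower reading cDBS follow-up is 30–45 days, close to one aDBS period, but the groups still differ through any losses at Setup or GIC.

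Parts of SAP 7.10 are redacted and could not be checked.

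**Conclusion.** The point holds as a limit on interpretation. The cDBS summary covers a wider group than the aDBS summary, the narrower group is selected partly on tolerability of aDBS, and time at risk differs. On the planning figures 40–50% of the cDBS group would appear under aDBS if LFP exits count, and about 66–100% if they do not, depending on how many are lost at Setup or GIC. The event percentages in the working rest on assumed risks. They show that a gap in either direction can arise with no true difference; they do not estimate its size. No confirmatory result is affected. The conflict between Protocol 9.7 and 9.8 is real and changes the cDBS denominator, and the As-Treated definition adds a phase name, the cDBS Baseline Evaluation Phase, that is not defined elsewhere. This is a cheap improvement worth making, not a flaw in the trial's main conclusions.

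**What to change.** In SAP 7.10 and Protocol 13.6:

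- Keep the all-subject As-Treated summary.
- For each aDBS mode actually received, add a cDBS Baseline summary limited to the subjects who entered aDBS Evaluation in that mode. Use the as-treated mode, because Protocol 9.10.1 and 9.10.2 foresee periods completed in the wrong mode.
- Give exposure days, or events per subject-time, in both phases.
- Add a within-subject cross-table per mode: event on cDBS only, aDBS only, both, neither.
- State with the table that these subjects were selected by the GIC; matching does not remove that selection. Report stimulation-related events during aDBS Setup and Adjustment beside it, so that events in GIC failures can be seen. They fall outside the two-phase summary, although the overall AE summary includes them.
- Reconcile Protocol 9.7, Protocol 9.8 and the phase name in the As-Treated definition, stating once whether LFP Screening exits count in the cDBS denominator.

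The cost is one extra table from data already collected, plus a wording correction. The matched table omits events in subjects who never entered Evaluation; these remain in the all-subject summary.
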